4 SUB-STUDY DESIGN

4.1 Design

This is a sub-study of a multi centre, two arm parallel, open label randomised controlled clinical trial, the Australian Placental Transfusion Study. Echocardiography will take place on all babies recruited to APTS over approximately a 12 month period at selected sites.

4.2 Subject Population

Preterm babies less than 30 weeks gestational age enrolled in the APTS study.

4.3 Enrolment to sub-study

All infants randomised to the main APTS study at a participating centre will be included in the substudy. If an echocardiographic fellow is temporarily not available, enrolment to the sub-study will be postponed for a pre-defined period while randomisation to the main study will continue.

4.4 Endpoints

Primary outcome:

Lowest systemic blood flow (defined as lowest recorded SVC flow of 3 measurements at 3, 9 and 24 hours after birth).

Secondary outcomes:

- 1. SVC flow recorded from echo assessments at 3 hours (range 3-5), 9 hours (range 6-12 hours) and 24 hours (range 20-28 hours) in babies less than 30 weeks gestation.
- 2. RVO recorded from echo assessments at 3 hours (range 3-5), 9 hours (range 6-12 hours) and 24 hours (range 20-28 hours) in babies less than 30 weeks gestation.
- 3. Ductal size and shunt direction in first 24 hours
- 4. Absolute change in haemoglobin / haematocrit concentration between baseline (from placenta at birth or, if unavailable, admission Hb/Hct) and at 6 hours after birth from baby
- Hypotension: incidence of persistent hypotension (>15 minutes) receiving treatment with volume expansion or inotropes or corticosteroids. Hypotension is defined as mean BP below the gestation in weeks (mmHg) [approximately <10th percentile for gestation and postnatal age].
- 6. Treatment with volume expansion in 1st 24 hours
 - Type and volume of volume expansion
- 7. Treatment with inotropes in 1st 24 hours
 - Type and dose of inotrope
- 8. Nitric oxide dose
- 9. Indomethacin
 - Timing of administration
- 10. Symptomatic patent ductus arteriosus
- 11. Late intraventricular haemorrhage defined as intraventricular haemorrhage on <14 day HUS not present on initial (3 hour) HUS

Page 43 of 81

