5.2.2 Blood Collection

Haemoglobin and haematocrit values should be collected at:

- · Baseline from cord bloods (where this is not possible, haemoglobin measures should be collected at admission)
- At 6 hours

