6 STATISTICS

6.1 Sample Size

242 babies yield 90 % power, assuming 2-sided significance (5%) and 20% noncompliance, to detect a relative increase of 27%, from a predicted 55 ml/kg/min in the early cord clamping infants to 70 ml/kg/min in the delayed cord clamping infants ². The sample size is calculated using log-transformed data, with a SD on the log scale of 0.21. All analyses will be performed using intention-to-treat principles.

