6.2 Statistical Analysis

The primary analysis will compare the mean SVC flow between the treatment arms using an independent sample t-test on log transformed data. Linear regression may be used as a secondary analysis in order to adjust for any important prognostic factors.

Effect sizes and 95% confidence intervals will be presented for primary and secondary outcomes. For continuous variables, ratios (retransformed mean differences) and 95% confidence intervals for log-transformed variables, differences in means (and standard deviation) or medians (interquartile range) and for dichotomous and categorical factors, relative risks, odds ratios and risk differences will be presented.

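### The echo sub-study's haemoglobin/haematocrit outcome is a raw change from baseline with no commitment to adjust for the cord value, which can only widen its interval

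*Supplement*

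**What the plan says.** The text is in the sub-study protocol, which is Appendix 1 of the latest protocol.

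- **Section 4.4, secondary outcome 4:** the outcome is the "Absolute change in haemoglobin / haematocrit concentration between baseline" and 6 hours. The two samples are described as "from placenta at birth or, if unavailable, admission Hb/Hct) and at 6 hours after birth from baby".
- **Section 5.2.2:** the first sample is "Baseline from cord bloods", with a fallback: "where this is not possible, haemoglobin measures should be collected at admission".
- **Section 6.2, effect measures:** primary and secondary outcomes get effect sizes and 95% confidence intervals. Log-transformed variables get ratios; other continuous variables get "differences in means (and standard deviation) or medians (interquartile range".
- **Section 6.2, adjustment:** the only mention of a model is in the paragraph on the primary SVC-flow comparison: "Linear regression may be used as a secondary analysis in order to adjust for any important prognostic factors". It is optional and names no factor.

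The only statistical analysis plan shown covers childhood follow-up and does not deal with this outcome.

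**The concern.** Followed as written, the plan subtracts each baby's baseline from the 6-hour value and compares the differences between arms. That treats a unit difference in the cord value as if it carried over in full to 6 hours. The two samples come from different sources (cord or placenta, then the baby), so there is no reason to expect a slope of exactly 1. If the slope is anything else, the subtraction adds variation that a regression on the cord value would remove.

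With a true cord baseline this costs precision and causes no bias: under randomisation both methods estimate the same arm difference. The admission fallback is a separate matter. That sample is taken from the baby after the intervention and can already contain part of the effect being measured.

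**Working it through.** **The plan's own figure.** No sample size, power or interval width is given for this outcome. The sub-study figure, "242 babies yield 90 % power, assuming 2-sided significance (5%) and 20% noncompliance", concerns SVC flow, "from a predicted 55 ml/kg/min in the early cord clamping infants to 70 ml/kg/min in the delayed cord clamping infants". It is approximately recovered on a log10 scale with the stated SD of 0.21. If 20% non-compliance dilutes the deferred mean to 70 − 0.2 × 15 = 67, the difference is log10(67/55) = 0.0857, and 121 per arm gives 88.8% power. On natural logs about 50 babies would suffice. Neither result bears on haemoglobin or haematocrit; only the 242 babies (121 per arm, taken as 1:1) are used below.

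**Variance comparison.** Let s0 and s6 be the SDs of the cord and 6-hour values and r their correlation. Per baby, within arm:

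- change score: s6² + s0² − 2·r·s0·s6
- linear model with cord value as covariate: s6²·(1 − r²)
- change score minus linear model: (s0 − r·s6)²

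The last line is never negative. It is zero only when r·s6/s0, the slope of the 6-hour value on the cord value, equals 1.

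**Size with equal SDs.** The documents give neither r nor the SDs, so r is assumed. The ratio of interval widths, adjusted to change score, is √((1 + r)/2). Adjusted analysis of 242·(1 + r)/2 babies matches the change score in 242, if every baby has a cord value.

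| Assumed r | Width ratio | Narrower by | Babies for equal precision |
|---|---|---|---|
| 0.3 | 0.806 | 19% | 157 |
| 0.5 | 0.866 | 13% | 182 |
| 0.7 | 0.922 | 8% | 206 |
| 0.8 | 0.949 | 5% | 218 |

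Simulation with 121 per arm gave ratios of 0.807, 0.869 and 0.924 at r = 0.3, 0.5 and 0.7.

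**Size with unequal SDs.** With k = s6/s0 the ratio is √(k²(1 − r²)/(1 + k² − 2rk)). At k = 1.2 and r = 0.5 this is √(1.08/1.24) = 0.933.

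| k | r = 0.3 | r = 0.5 | r = 0.7 |
|---|---|---|---|
| 0.8 | 0.709 | 0.756 | 0.792 |
| 1.2 | 0.873 | 0.933 | 0.983 |
| 1.5 | 0.933 | 0.982 | 0.999 |

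At k = 1.2 the gain is thus about 13%, 7% and 2%. At k = 1.25 and r = 0.8 the slope is 1 and the gain is nil.

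**On the haematocrit scale (illustration only).** The childhood follow-up proposal, section 4.2, gives SDs of 7.3 and 8.2 for peak first-week haematocrit, which is a different measurement. With their midpoint, 7.75, and r = 0.5:

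- change score: 1.96 × 7.75 × √(2 × 0.5) × √(2/121) = 1.95 points half-width
- adjusted: 1.96 × 7.75 × √0.75 × √(2/121) = 1.69 points

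At r = 0.3 the figures are 2.31 and 1.86, and ignoring baseline altogether gives 1.95. Below r = 0.5 (equal SDs) the change score is less precise than an unadjusted 6-hour comparison.

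**The admission fallback.** Suppose a fraction q of babies use the admission value, which already carries a fraction f of the true effect D, and the slope is b. The change score then estimates D(1 − qf) and the adjusted model D(1 − bqf). Take D = 3.1 (the peak-haematocrit difference in the same section) and assume q = 0.3, f = 1 and b = 0.5. The results are 3.1 × 0.70 = 2.17 and 3.1 × 0.85 = 2.64 (simulated: 2.18 and 2.65). Both are pulled towards zero, so adjusting for the admission value is no remedy.

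**The case against.** **The wording defines a variable, not a model.** Section 4.4 does not forbid a baseline covariate. A baseline-adjusted model also yields a difference in means, and regressing the change on baseline gives the same treatment estimate as regressing the 6-hour value. Covariates for one of eleven secondary outcomes might be left to a sub-study analysis plan, and none is shown. It stands that nothing is barred and that the endpoint can keep its name. But the text, followed literally, gives an unadjusted comparison of changes, and no document shown commits to anything else.

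**The size is assumed.** This stands in full. Correlation, SDs and the number of missing cord samples are all absent from the documents, and a baby without a cord value gains nothing from the covariate. A reader might infer that adjustment makes 242 babies worth some 285 to 372 analysed by change score (242 divided by (1 + r)/2 at r = 0.7 and 0.3). That needs equal SDs, those correlations and a cord sample from every baby.

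**The importance is limited.** A reader might also infer that precision here is critical because the pilot found no haemoglobin difference, or because this is the only check that a transfusion took place. The documents support neither. The pilot result was a 6-hour level, not a change, in 40 babies over four arms. The main trial records peak haematocrit in the first 7 days and clamping duration, and the follow-up proposal already reports a 3.1-point haematocrit difference in 488 infants.

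**Timing of the cord sample.** The documents do not say whether it is drawn before or after clamping. Using it as covariate assumes that allocation does not affect it, which the sponsor should confirm.

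**Conclusion.** The point holds as an inexpensive gain in precision for one secondary sub-study outcome. The direction is certain: one degree of freedom aside, the raw change is never more precise than the cord-adjusted comparison, and it is less precise unless the slope is 1. The size is not certain. The range of about 19% to 5% rests on an assumed correlation of 0.3 to 0.8, equal SDs and complete cord samples. A moderately larger 6-hour SD or missing cord samples would reduce it; a smaller 6-hour SD would increase it. The admission fallback can bias the estimate towards zero, by an amount that depends on how often it is used and how much effect it already carries; the documents give neither. No stated power claim depends on this outcome, and neither the SVC-flow analysis nor the main trial is affected.

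**What to change.** In sections 4.4 and 6.2 of the sub-study protocol, name as the main analysis of secondary outcome 4 the arm difference in the 6-hour value (equivalently, in the change) from a linear model with the cord or placental value as covariate, with its 95% interval. In addition:

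- Do not use the admission value in place of a missing cord value, either as covariate or for subtraction.
- Report missing cord samples by arm. Sampling follows allocation in an open-label trial, so missingness could differ between arms. Keep babies without a cord value through a missing-baseline indicator only if it does not.
- Give the unadjusted 6-hour comparison in all babies as a sensitivity analysis.

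The cost is a few sentences and one count by arm. No new data are needed, and the endpoint can keep its name.

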5 TREATMENT OF PARTICIPANTS

Deferred cord clamping is performed against the background of usual care^{24, 25}. For example, the timing of parenteral administration of uterotonic or the use of plastic wrap to warm the baby would be according to existing local protocols with no changes required for the study.

(a) Immediate cord clamping (< 10 seconds after birth)

• The cord is clamped 6 cm from the umbilicus within ten seconds of delivery of the baby.

(b) Deferred cord clamping

• A birth attendant holds the baby as low as possible below the level of the introitus or placenta for 60 seconds or more, then clamps the cord about 6 cm from the umbilicus.

Variation from the recommended procedures should be undertaken whenever this is judged necessary by the responsible clinician(s) acting in the best interests of the mother or baby. If the baby is *in extremis* or non-vigorous, the attending clinicians may use their discretion in administering the intervention.^{24, 25}

There is concern that palpating the cord may restrict blood flow from placenta to infant. Therefore auscultation is encouraged rather than palpating the cord, subject to the clinician's discretion.

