7.6 As for main study Data Handling and Record Keeping	
7.7 Study Monitoring	
7.8 Audit and Inspection	
7.9 Clinical Study Report	
7.10 Publication Policy	
8 LIST OF APPENDICES	
Appendix 1: Measurements.	
9 REFERENCES	

1 SYNOPSIS

Aim:

The primary question is: does placental transfusion decrease or increase the risk of low systemic flow, determined by echocardiography in the first 24 hours after birth?

Clinical hypotheses:

Placental transfusion is associated with higher systemic blood flow in the first 24 hours.

Study design:

Sub-study of multi-centre, open label, randomised controlled trial

Study population:

Preterm babies less than 30 weeks gestational age enrolled in the APTS study.

Study assessments

Echocardiography and cardiorespiratory measurements performed at 3, 9 and 24 hours after birth.

Blood collection for Hb/HCT at birth (cord blood) and 6 hours.

Primary Outcome

Lowest SVC flow in 1st 24 hours – this is the lowest SVC recorded from echo assessments at 3 hours (range 3-5), 9 hours (range 6-12 hours) and 24 hours (20 – 28 hours).

Summary statistical methods

242 babies yield 90 % power, assuming 2-sided significance (5%) and 20% noncompliance, to detect a relative difference of 27% - from 55 ml/kg/min in the early cord clamping infants to 70 ml/kg/min in the delayed cord clamping infants ². Additional power will be obtained by further enrolments according to echo substudy resources at individual centers until completion of the main APTS study.

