There is also evidence of potential harm from excessive use of volume expansion in preterm infants with observational studies reporting an association with PIVH ³⁶ and chronic lung disease³⁹ in preterm infants receiving volume expansion. A systematic review of albumin infusion in critically ill patients of all ages including those with hypovolaemia, burns and hypoalbuminemia found significantly increased mortality in patients receiving albumin compared to control.⁴⁰ Systematic reviews of randomised trials of early volume expansion in preterm infants¹² and early volume expansion versus inotropes in preterm infants¹¹ found that there is no evidence to support the routine use of early volume expansion in preterm infants in the first day, and that volume expansion is less effective than inotropes (dopamine) at increasing BP in hypotensive very preterm infants.

Evidence for placental transfusion

Systematic review of trials of delayed cord clamping^{6, 7, 15} have demonstrated a significant reduction in the incidence of transfusion for low blood pressure (2 studies; 58 infants; RR 0.38, 95% CI 0.18, 0.84) and several neonatal morbidities related to low systemic blood flow including IVH (10 studies; 436 infants; RR 0.54, 95% CI 0.37, 0.78) and NEC (6 studies, 281 infants; RR 0.61, 95% CI 0.43, 0.88).^{6, 7, 15}

In an observational study² of infants born <30 weeks gestation with early and delayed cord clamping (at discretion of neonatologist), median flow in the SVC in the first 24 hours was significantly higher in the group with delayed clamping (median 91 ml/kg/min; IQR 81–101) compared with 52 ml/kg/min (IQR 42–100) in the immediate clamping group (p=0.028). Fewer infants in the delayed group had low flow <55ml/kg/min (1 compared with 9; p=0.017). All three infants with IVH had low flow.

Outcome	No. of RCTs	No. of babies	Effect type	Estimate (95% confidence interval)
Potential benefits				intervaly
Haematocrit* 1 hr after birth	6	281	WMD ^T	3.00 [1.49, 4.51]
Haematocrit* 4 hr after birth	4	134	WMD	5.40 [3.52, 7.28]
Number of blood transfusions	5	212	WMD	-1.32 [-1.93, -0.70]
• Transfused for low blood pressure	2	58	RR ^	0.38 [0.18, 0.84]
Intraventricular haemorrhage (IVH)	10	436	RR	0.54 [0.37, 0.78]
Necrotising enterocolitis (NEC)	6	281	RR	0.61 [0.43, 0.88]
Late onset sepsis (LOS)	1	72	RR	0.1 [0.01, 0.85]
Mortality	11	480	RR	0.84 [0.43, 1.63]
• Temperature on admission (°C) [#]	3	143	WMD	0.14 [-0.03, 0.31]
Potential adverse effects				

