• Peak serum bilirubin (micromol/L)	7	320	WMD	11.13 [1.75, 20.51]

Table 1: Effects of placental transfusion versus early clamping in 11 RCTs, 494 babies < 37 wks	gestation:

* packed cell volume; ^T WMD weighted mean difference; ^ Relative risk; [#] Rabe et al., 2008

Page 42 of 81

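### The sub-study's haemoglobin/haematocrit change allows the baby's admission sample as baseline, so for those babies any treatment effect already present at admission is subtracted from the outcome

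*Supplement*

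**What the plan says.** The sub-study protocol is the appendix to main protocol V4.0. Section 4.4 lists secondary outcome 4 as the change in haemoglobin or haematocrit "between baseline (from placenta at birth or, if unavailable, admission Hb/Hct) and at 6 hours after birth from baby". Section 5.2.2 repeats the rule: "Baseline from cord bloods (where this is not possible, haemoglobin measures should be collected at admission"). The sub-study synopsis gives only the intended samples, "Blood collection for Hb/HCT at birth (cord blood) and 6 hours", and the schedule in section 5.1 likewise marks blood sampling at birth and 6 hours, with no admission column or time window.

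Section 5 of the main protocol fixes when the intervention happens. In the control arm, "The cord is clamped 6 cm from the umbilicus within ten seconds of delivery of the baby". In the deferred arm the baby is held low "for 60 seconds or more, then clamps the cord about 6 cm from the umbilicus".

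Section 6.2 of the sub-study specifies a t-test on log SVC flow, an optional regression adjusting for prognostic factors, and the effect measures to report. It has no rule for combining the two kinds of baseline and does not name the 6-hour value as an outcome in its own right. The follow-up SAP does not cover this outcome.

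**The concern.** A change score measures a treatment effect cleanly only if the value subtracted could not have been affected by treatment. Cord or placental blood is a reasonable candidate. A sample from the baby on admission is not, because in both arms clamping is over by then and a deferred-arm baby has already received whatever placental blood it was going to receive.

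The sub-study's own background indicates an early effect. Its Table 1 ("Effects of placental transfusion versus early clamping in 11 RCTs, 494 babies" under 37 weeks) reports a between-arm haematocrit difference at 1 hour and a larger one at 4 hours. Any part of that difference present at admission enters the baseline of deferred-arm babies on the fallback and is taken away from their change. The arms could also end up with different mixtures of pre- and post-intervention baselines, and nothing in the analysis section would show it.

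At stake is the reading of one secondary outcome. A diluted or distorted difference at 6 hours could be taken as the real early haematological effect of deferred clamping.

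**Working it through.** The plan states no figure for this outcome, so there is nothing to reproduce. The check has two parts: the order of events, and an illustration of size.

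**Order of events.** Clamping takes place within 10 seconds of delivery or at 60 seconds or more. Admission comes after delivery is complete. The fallback baseline is therefore post-intervention for every baby who uses it, in both arms.

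**Notation**
- D6: between-arm difference in the baby's haematocrit at 6 hours.
- Da: between-arm difference already present at admission.
- c: average change from the cord or placental value to the admission value in control babies, unrelated to treatment.
- f_I, f_D: shares on the fallback in the immediate and deferred arms.
- H6: mean 6-hour value in the control arm. B0: mean cord or placental value, assumed equal in the two arms.

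**Formula**
- Mean change, immediate arm = (H6 − B0) − f_I·c
- Mean change, deferred arm = (H6 + D6 − B0) − f_D·(c + Da)
- Difference = D6 − f_D·Da − c·(f_D − f_I)

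The second term is the effect subtracted out. The third vanishes when the fallback is equally common in both arms.

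**Inputs.** Table 1 of the sub-study gives 3.00 (95% CI 1.49 to 4.51; 6 trials, 281 babies) at 1 hour and 5.40 (3.52 to 7.28; 4 trials, 134 babies) at 4 hours. I take Da = 3.00 and D6 = 5.40. Both are proxies: no admission time is stated, and 6 hours is not tabulated. The fallback share is not given, so it is varied.

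**Equal fallback use (f_I = f_D = f): difference = 5.40 − f·Da**

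| f | Da = 3.00 | loss at Da = 3.00 | Da = 1.49 | Da = 4.51 |
|---|---|---|---|---|
| 0% | 5.40 | 0% | 5.40 | 5.40 |
| 10% | 5.10 | 0.30/5.40 = 6% | 5.25 | 4.95 |
| 25% | 4.65 | 0.75/5.40 = 14% | 5.03 | 4.27 |
| 50% | 3.90 | 1.50/5.40 = 28% | 4.66 | 3.15 |
| 100% | 2.40 | 3.00/5.40 = 56% | 3.91 | 0.89 |

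The admission effect may be smaller than any of these. If Da were 1.0 (an assumption), f = 20% would cost 0.20/5.40, about 4%, against 0.60/5.40 = 11% with Da = 3.00.

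**Unequal use (assumed shares of 10% and 40%, Da = 3.00)**
- f_D = 40%, f_I = 10%: 5.40 − 1.20 − 0.30c = 4.20 − 0.30c. A natural early rise (c > 0) deepens the attenuation.
- f_D = 10%, f_I = 40%: 5.40 − 0.30 + 0.30c = 5.10 + 0.30c. This exceeds 5.40 once c is above 0.30/0.30 = 1.00 point, so the bias would then exaggerate the effect.

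The direction is therefore settled only when fallback use is similar in the two arms.

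**The case against.** The strongest reply is that the consequence is small and its size cannot be known. Cord blood is the default and admission only a substitute, so f may be low. The outcome is a concentration, not a red-cell mass. Section 1 of the main protocol suggests that fluid shifts or diuresis after the transfusion may explain the rise at 1 and 4 hours. On that account an early admission sample could contain the transfused cells yet show little of the rise, and Da could be well under 3.00. The two tabulated differences also come from different sets of trials in babies under 37 weeks. All of this stands: the percentages above are illustrations, not estimates.

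A reader might also infer that this outcome is the sub-study's check that a transfusion was delivered, so that the SVC result cannot be interpreted without it. The documents do not support that. No section gives it that role. Clamp time and the height at which the baby is held are recorded and monitored centrally (main protocol 5.1). Peak haematocrit in the first 7 days is a main-trial tertiary outcome (3.4.5). The follow-up funding application (4.2) shows clamp time and peak haematocrit being reported by arm. None of these uses the disputed baseline, and neither does lowest SVC flow.

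A further tempting step is that the deferred arm must use the fallback more often because less blood is left in the placenta. That is plausible but is not stated anywhere.

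The reply does not remove the defect: the substitute baseline is post-intervention by construction, and no analysis rule handles it.

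**Conclusion.** The concern holds in a limited form. For babies on the admission fallback, secondary outcome 4 subtracts any treatment effect already present at admission. With similar fallback use in both arms, the between-arm difference is biased towards no effect. This assumes that the admission effect has the same sign as the 6-hour effect and that cord or placental concentration does not differ by arm. With unequal use, bias of either sign can be added, so the bias cannot be described as always conservative.

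The amount cannot be determined from the documents. On the proxy inputs it runs from about 6% of the effect at f = 10% to 28% at f = 50%. The 56% figure needs every deferred-arm baby to be on the fallback and the full 1-hour difference to be present at admission, which nothing in the documents suggests. The matter is confined to one secondary outcome of the sub-study. It is still worth correcting, because the remedy needs no new data.

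**What to change.** In sub-study sections 4.4 and 5.2.2:

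- Redefine outcome 4 as haemoglobin/haematocrit in the baby at 6 hours, compared between arms as randomised in all sub-study babies. The pilot described in section 1 of the main protocol already compared haemoglobin at this time.
- Allow the cord or placental value as an optional baseline covariate. Keep the unadjusted comparison as the main result, since the covariate will be missing for some babies.
- Stop using the admission value as a substitute baseline. Where collected, report it as a post-intervention measurement, with its time.
- Report by arm how many babies had a cord or placental sample, an admission sample only, or neither.
- If change from cord blood is still wanted in babies who have that sample, present it as descriptive only. Whether a sample exists is determined after randomisation and may differ by arm, so this subset is not protected by randomisation and does not fit the intention-to-treat principle in section 6.1.

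The cost is a wording change and one extra table row. The 6-hour sample is already in the schedule, and a baby without it could not contribute to the change score either. What is lost is the within-baby change for babies without cord blood.
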